8.1 Extent of Exposure

All tabulations will be prepared for the Safety analysis set.

8.1.1 IMP (Gonadotropins)

Exposure to gonadotropins will be summarized as the total gonadotropin dose administered, dose administered from day 6 to last stimulation day, duration of treatment (days). Frequency tables will be included to describe the duration of treatment, the maximum dose, the dose on stimulation day 6, the final dose, and the number of dose adjustments.

This table will be produced overall and for subjects who completed the stimulation cycle, i.e. underwent triggering of final follicular maturation.

8.1.2 GnRH Antagonist

Once both the lead follicle measures ≥ 14 mm and serum E2 levels are ≥ 300 pg/mL, the GnRH antagonist (ganirelix acetate) will be initiated at a daily dose of 0.25 mg and continued throughout the gonadotropin treatment period.

The total dose, starting day of GnRH antagonist, and duration of treatment (days) will be tabulated. This table will be produced overall and for subjects who completed the stimulation cycle, i.e. underwent triggering of final follicular maturation.

8.1.3 hCG

A single injection of 250 μ g hCG (Ovidrel[®]) will be administered to induce final follicular maturation as soon as 3 follicles of ≥ 17 mm are observed on TVUS. The following will be tabulated: number of subjects who met the hCG criteria, number of subjects that had hCG administered, number of subjects who met the hCG criteria and had hCG administered, the number of days from when the hCG criteria was met to when the hCG administered, and the number of subjects who had the hCG trigger replaced with a GnRH agonist trigger.

8.1.4 Progesterone

Vaginal progesterone inserts (200 mg/day – ENDOMETRIN[®]; Ferring) will be initiated for luteal phase support and will continue until the day of the β -hCG test (10-14 days after blastocyst transfer) if negative for pregnancy or if pregnancy is confirmed, will be continued for a maximum of 10 weeks.

The total dose and duration of treatment (days) will be tabulated for all subjects, for subjects with two positive β -hCG, and for subjects that do not have two positive β -hCG results.

8.2 Treatment Compliance

As treatment compliance is assumed to be high, only subjects not receiving the scheduled dose will be listed by center and subject number.

Separate listings will be prepared for

- violations of the IMP schedule
- violations of the antagonist schedule
- hCG not administered according to the protocol
- Agonist not administered according to the protocol
- Progesterone not administered according to the protocol

In addition, a summary table displaying the number and frequency of subjects with violations of the IMP schedule, violations of the antagonist schedule, hCG not administered according to the protocol, agonist not administered according to the protocol and progesterone not administered according to the protocol will be presented.

9 Efficacy

9.1 General Considerations

Efficacy analysis will be conducted for the mITT population unless otherwise specified. All statistical tests will be performed using a two-sided test at a 5% significance level. No adjustments will be made for multiple tests. Baseline for all efficacy analyses will be the values obtained at the last assessment prior to the first dose of IMP.

9.1.1 Tabulations

All summaries will be presented by treatment group and overall. Categorical data will be summarized using numbers and percentages. The percentages are based on the total number of subjects with a corresponding assessment. Continuous data will be presented using the number of subjects with an observation, mean and standard deviation, median, interquartile range, minimum, and maximum.

9.1.2 Listings

All primary and secondary endpoints will be listed sorted by center, treatment, and subject id.

9.1.3 Handling of Drop-Outs and Missing Values

For the primary and secondary endpoints positive β -hCG and clinical pregnancy missing observations will be imputed to negative unless a positive result is observed at a later pregnancy assessment. For example, if the outcome of β -hCG is missing but clinical pregnancy is 'positive' then β -hCG will be imputed as 'positive'.

Missing values will not be imputed for the any of the other secondary endpoints.

9.2 Primary Endpoint

The primary objective of the trial is to demonstrate that MENOPUR[®] is non-inferior to recombinant FSH with respect to ongoing pregnancy rate in a single fresh treatment cycle following a GnRH antagonist protocol. Ongoing pregnancy is defined as presence of at least 1 intrauterine pregnancy with a detectable fetal heartbeat at 10-11 weeks gestation (8-9 weeks after blastocyst transfer in the fresh cycle). The non-inferiority limit for the difference between treatments (MENOPUR[®] minus Gonal-f[®]) is -12% (absolute). The non-inferiority hypothesis to be tested for the primary endpoint is:

$$H_0: \pi_{\text{MENOPUR}} - \pi_{\text{Gonal-f}} \leq -12\%$$

against the alternative

$$H_1: \pi_{\text{MENOPUR}} - \pi_{\text{Gonal-f}} > -12\%,$$

where π_{MENOPUR} and $\pi_{\text{Gonal-f}}$ denote the ongoing pregnancy rate of subjects treated with MENOPUR[®] and Gonal-f[®], respectively, in a single fresh embryo transfer following a GnRH antagonist protocol.

The null hypothesis (H_0) will be tested against the alternative by constructing a 2-sided 95% confidence interval for the difference in ongoing pregnancy rates. If the lower-limit of the 95% confidence interval is greater than the non-inferiority limit (-12%), the null hypothesis will be rejected and it would be claimed that MENOPUR® is non-inferior to Gonal-f® with respect to ongoing pregnancy rate in a single fresh embryo transfer following a GnRH antagonist protocol.

If the 95% confidence interval for the treatment difference not only lies above the non-inferiority limit (-12%) but also above zero then there is evidence of superiority in terms of statistical significance at the 2-sided 5% level. With evidence of superiority, the corresponding 2-sided p-value will be reported. There is no need for a multiplicity adjustment since it is a simple closed test procedure.

Due to the expected large sample size, the confidence interval will be established based on the asymptotic normal distribution as follows:

$$\hat{\pi}_{MENOPUR} - \hat{\pi}_{Gonal-f} \pm Z_{(1-\alpha/2)} \sqrt{\frac{\hat{\pi}_{MENOPUR}(1-\hat{\pi}_{MENOPUR})}{N_{MENOPUR}} + \frac{\hat{\pi}_{Gonal-f}(1-\hat{\pi}_{Gonal-f})}{N_{Gonal-f}}}$$

where

$\hat{\pi}_{MENOPUR}$: is the observed ongoing pregnancy rate of subjects randomized to MENOPUR® in a single fresh treatment cycle following a GnRH antagonist protocol.

$\hat{\pi}_{Gonal-f}$: is the observed ongoing pregnancy rate of subjects randomized to Gonal-f® in a single fresh treatment cycle following a GnRH antagonist protocol.

$N_{MENOPUR}$: is the number of subjects randomized to MENOPUR®.

$N_{Gonal-f}$: is the number of subjects randomized to Gonal-f®.

$Z_{(1-\alpha/2)}$: is the 1- $\alpha/2$ percentile in the standard normal distribution.

α : is the significance level, i.e., 0.05.

Subjects who do not have at least 1 intrauterine pregnancy with a detectable fetal heartbeat at 10–11 weeks gestation (8-9 weeks after blastocyst transfer in the fresh cycle) due to missing data, early withdrawal, or any other reason will be considered treatment failures (i.e., not having ongoing pregnancy) unless they have an assessment of detectable fetal heartbeat at a later date. Hence, for the analysis of this endpoint all positive (detectable fetal heartbeat) ultrasound assessments that occur in the interval from the end of 7th week from fresh transfer till the end of study will be considered as responder for the primary endpoint (i.e., ultrasound assessment date – fresh transfer date + 1 \geq 7 *7 = 49). Forty nine days was used because the 8-9 weeks visit window included 50

(beginning of the 8th week) to 63 days after fresh transfer. The primary endpoint analysis will be based on the mITT analysis set.

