2.2 Endpoints

Primary Endpoint

• Ongoing pregnancy rate, defined as the presence of at least 1 intrauterine pregnancy with a detectable fetal heartbeat at 10–11 weeks of gestation (8-9 weeks after blastocyst transfer in the fresh cycle).

Secondary Endpoints

- Positive β-hCG rate (2 positive β-hCG tests; the first approximately 10-14 days after blastocyst transfer in the fresh cycle and a second confirmatory test approximately 2 days later).
- Clinical pregnancy rate (transvaginal ultrasound [TVUS] showing at least 1 intrauterine gestational sac with fetal heart beat at 6-7 weeks gestation, 4-5 weeks after blastocyst transfer in the fresh cycle).
- Early pregnancy loss (defined as 2 positive β-hCG tests but no ongoing pregnancy at 10-11 week's gestation in the fresh cycle).

Trial Code: 000205

Date: 10 Dec 2015

E-Protocol Amendment-19588; Ver. 1.0

Supersedes: 28 October 2015

Page 16 of 69

- Follicular development as assessed by TVUS (total number of follicles and number of follicles with a diameter of ≤ 9 mm, 10-11 mm, 12-14 mm, 15-16 mm, and ≥ 17 mm on stimulation Day 6 and the last day of stimulation).
- Endocrine profile:
 - Serum follicle-stimulating hormone (FSH), hCG, luteinizing hormone (LH), androstenedione, total testosterone, dehydroepiandrosterone (DHEA): Day 1, Day 6, and last day of stimulation.
 - Progesterone (P4), estradiol (E2): Day 1, Day 6, last day of stimulation, and Visit 4 (morning following hCG administration).
- Oocytes retrieved metaphase II oocytes, number of oocytes undergoing ICSI, fertilization
 rate, quality of embryos 3 days after oocyte retrieval, and the quality of blastocysts 5 days
 after oocyte retrieval.
- Aneuploidy rate.
- Endometrial assessment by TVUS (endometrial thickness in mm and echogenicity pattern on stimulation Day 6, the last day of stimulation, and at the time of blastocyst transfer in the fresh cycle [transabdominal pelvic ultrasound or TVUS]).

Post-trial Endpoints

- Cumulative live birth rate for fresh and frozen blastocyst transfers (viable live birth >21 weeks gestation).
- Live birth rate for fresh blastocyst transfers (viable live birth >21 weeks gestation).
- Early pregnancy loss rate in frozen blastocyst transfer, defined as 2 positive β-hCG tests but no ongoing pregnancy at 10-11 weeks gestation in the frozen cycle.
- Late pregnancy loss rate (defined as a confirmed ongoing pregnancy but no live birth).

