6.4 Visit 4 - Day Following Administration of Ovidrel®

The subject will return to the center (in the morning) the day following the Ovidrel[®] injection for P4 and E2 samples to be submitted to the central laboratory; serum hCG will be analyzed at the local lab. A TVUS will be performed. The date, time, and dosage of Ovidrel[®] will be recorded as well as study medication compliance. Adverse events and concomitant medications will be assessed and documented. Any symptoms of OHSS will be closely monitored.

The cycle will be cancelled in case of poor ovarian response (if the Investigator judges that ≥ 3 follicles of ≥ 17 mm cannot be reached after a minimum of 10 days of stimulation).

Subjects who have an excessive response to ovarian stimulation (>30 follicles of ≥12 mm and/or E2 ≥5000 pg/mL) will have the fresh transfer cancelled, and the hCG trigger will be replaced with a GnRH agonist trigger (4 mg leuprolide acetate). If leuprolide acetate is administered, a blood sample for LH will be collected and analyzed at the local lab. All resultant expanded blastocysts will be vitrified after trophectoderm biopsy, with no fresh blastocyst transfer in order to decrease the risk of OHSS. Following oocyte retrieval and blastocyst evaluation, an End of Trial (EOT) Visit will be scheduled or completed and the information will be documented in the eCRF.

In order to minimize the risk of empty follicle syndrome, the subject will return the morning after hCG trigger to draw serum hCG, E2, and P4 levels. If the hCG level is <50 IU/L and/or P4 is <3.5 ng/mL, then a booster/rescue second dose of hCG must be given on that day as soon as possible. If the subject received the GnRH agonist trigger, the bloods drawn will be LH, E2, and P4 levels. If, after the GnRH agonist trigger, the LH is <15 IU/L and/or the P4 <3.5 ng/mL, a rescue/booster dose of hCG (Ovidrel®) should be given as soon as possible. Delay of oocyte retrieval will be left to the clinician's discretion and will be based on the time at which the rescue dose was administered.

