6.7 Visits 7, 8, and 9 - Pregnancy Monitoring

- Visit 7: All subjects will be required to return to the clinic approximately 10-14 days after blastocyst transfer for β-hCG assessment. If the first serum β-hCG is positive, a second confirmatory test will be performed approximately 2 days later. If the pregnancy test is negative, ENDOMETRIN[®] will be discontinued and EOT procedures completed. If conflicting results are obtained in the first 2 tests, a third test will be performed 2 days after the second test. If a positive β-hCG is confirmed, ENDOMETRIN [®] will continue up to 10 weeks from the time it was initiated until the EOT Visit.
- **Visit 8**: Subjects who are pregnant will return to the clinic 4-5 weeks after blastocyst transfer for clinical pregnancy assessment (TVUS showing at least 1 intrauterine gestational sac with fetal heartbeat).

Trial Code: 000205

Date: 10 Dec 2015

E-Protocol Amendment-19588; Ver. 1.0

Supersedes: 28 October 2015

Page 35 of 69

• **Visit 9:** Subjects with clinical pregnancy will return to the clinic 8-9 weeks after blastocyst transfer for assessment of ongoing pregnancy (presence of at least 1 intrauterine pregnancy with a viable fetus with a detectable fetal heartbeat).

An End of Trial (EOT) Visit will be scheduled or completed for non-pregnant subjects and the information will be documented in the eCRF.

Non-pregnant subjects: Subjects without 2 positive β -hCG tests, clinical pregnancy, or ongoing pregnancy in the fresh cycle, may undergo a single frozen blastocyst transfer within 6 months of each subject's date of randomization. The PGS results can be used to select the euploid blastocyst for frozen transfer. Frozen-thawed blastocyst transfer cycle data will be collected, including blastocyst transfer information (endometrial thickness and echogenicity, grade of blastocyst, ploidy of blastocyst, presence of blood, or mucus within catheter tip), β -hCG serum results, clinical pregnancy, and ongoing pregnancy for the first frozen blastocyst transfer cycle following negative pregnancy.

Subjects may also return to the study center for regularly scheduled clinic visits as required per study center standard of care. The data collected during these visits will not be documented in the eCRF unless it is new or is a change in concomitant medications, pregnancy, or AEs.

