8.3 Pregnancy and Pregnancy Outcome

Subjects who achieve pregnancy (2 positive β -hCG tests) will be followed for clinical pregnancy (intrauterine gestational sac and/or fetal heart movement approximately 4-5 weeks after embryo transfer) and ongoing pregnancy (approximately 8-9 weeks after embryo transfer). Pregnant subjects will complete their final study visit approximately 8-9 weeks after embryo transfer (or sooner, if there is a loss of pregnancy). Subjects with ongoing pregnancy will be followed by telephone or mail for live birth data and information will be recorded in the eCRF. Pregnancy loss will be recorded on a pregnancy follow-up form in the eCRF.

Trial Code: 000205 Date: 10 Dec 2015 E-Protocol Amendment-19588; Ver. 1.0

Supersedes: 28 October 2015 Page 47 of 69

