9 STATISTICAL METHODS

This section details the planned statistical analyses for the primary endpoint and outlines the secondary endpoints. All analyses and further descriptions of the statistical methodology for the primary and secondary endpoints will be included in the Statistical Analysis Plan available before the first subject signs their informed consent. Any deviations from the protocol-specified statistical analysis will be described in the Statistical Analysis Plan or final report, as appropriate. A separate Statistical Analysis Plan will be prepared to cover the post-trial information.

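### SAP 9.2's responder rule does not match its own endpoint definition: it opens 1 to 2 days before its stated window and does not tie the heartbeat to the fresh-transfer pregnancy, and SAP 9.3.2 has the same faults plus a timing that differs from the protocol

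*SAP*

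**What the plan says.** Protocol 2.2 sets the primary endpoint at 10–11 "weeks of gestation (8-9 weeks after blastocyst transfer in the fresh cycle"), and SAP 9.2 repeats this. The SAP states its aim as the "ongoing pregnancy rate in a single fresh treatment cycle following a GnRH antagonist protocol" and defines both estimated rates on that basis.

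SAP 9.2 then treats a woman without a heartbeat at that time as a failure unless one is seen later. From this it derives the working rule: every positive ultrasound counts "that occur in the interval from the end of 7th week from fresh transfer till the end of study will be considered as responder", with scan date − fresh transfer date + 1 ≥ 49. The reason given is: "Forty nine days was used because the 8-9 weeks visit window included 50" (the start of week 8) to 63 days.

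The SAP change log (version 4.0) explains that some primary-endpoint visits took place up to 4 weeks early. It says that a visit window is now defined and that later positives also count. SAP Section 12 lists only positives after the 8–9 week window, and describes them as pregnancy tests, not heartbeats.

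SAP 9.3.2 gives clinical pregnancy the same kind of rule, with a bound of 14. SAP 2.2 and 9.3.2 place that endpoint at 5–6 weeks' gestation, 3–4 weeks after transfer. Protocol 2.2 places it at 6–7 weeks' gestation, 4–5 weeks after transfer.

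**The concern.** This rule, not the definition, decides who is a responder. Three things do not fit.

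1. **Lower bound.** The stated exception is for a heartbeat seen later than the endpoint time, yet the formula built on it opens earlier than the window cited to justify it. A heartbeat seen before the defined time can count with no later confirmation, and Section 12 does not disclose the early opening.
2. **Link to the fresh pregnancy.** The fresh transfer serves only as a time origin. The end of study is not defined; SAP 7.3 and 10.2 refer instead to the end-of-trial visit. Protocol 3.1.2 allows frozen transfers within 6 months of randomization and collects their pregnancy outcomes, so data that could be misclassified will exist. SAP 9.1.3 and 9.3.1 also accept a later positive assessment without saying which transfer it must come from.
3. **Clinical pregnancy.** The SAP says it is based on the 10 December 2015 protocol but times this endpoint a week earlier, and Section 12 does not list the change.

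At stake is whether the primary comparison measures what it claims to measure, and whether two programmers would derive the same responders.

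**Working it through.** **The plan's own figures.** Counting the transfer day as day 1, week 7 ends on day 7 × 7 = 49, and weeks 8 and 9 run from day 50 to day 63. So 49 and 50–63 both reproduce, as ordinal weeks.

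**Opening of the primary rule.** Difference + 1 ≥ 49 means at least 48 elapsed days. Day 50 is 49 elapsed days on the same count, or 50 if it means days after transfer. The rule therefore opens 49 − 48 = 1 day or 50 − 48 = 2 days early.

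**Gestational age at 48 elapsed days.** The documents map 8–9 weeks after transfer to 10–11 weeks' gestation, a 14-day offset. A 19-day offset (retrieval at 2w0d plus 5 days) is an assumption; the documents do not state it.

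| Offset | Age at 48 elapsed days | 10w0d (70 days) reached at | Gap, completed weeks | Gap if the 10th week starts at 9w0d (63 days) |
|---|---|---|---|---|
| 14 days | 62 days = 8w6d | 56 elapsed | 8 days | 49 − 48 = 1 day |
| 19 days (assumed) | 67 days = 9w4d | 51 elapsed | 3 days | none (44 elapsed) |

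**Clinical pregnancy (SAP 9.3.2).** Difference + 1 ≥ 14 means 13 elapsed days. The SAP's window starts at day 15, which is 14 or 15 elapsed days, so this rule also opens 1–2 days early. The protocol's 4 weeks is 28 days, and 28 − 13 = 15 days.

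**Does the day bound alone exclude frozen cycles?** No. For illustration, take a frozen transfer 28 days after the fresh one. Scans 4–5 weeks later fall at 56–63 elapsed days and scans 8–9 weeks later at 84–91, all past 48.

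**Illustration of the literal frozen-cycle reading, which is unlikely.** Inputs are 300 per arm (Protocol synopsis), a Gonal-f rate of 50% (SAP 3.2), and a MENOPUR rate of 50 − 12 = 38%. Let t be the share of fresh-cycle failures that had a fresh transfer, and q the share of those with a later frozen-cycle heartbeat. The documents give neither. Rates become 0.38 + 0.62tq and 0.50 + 0.50tq. With d the difference between them, P(false non-inferiority) = Φ((d + 0.12)/SE − 1.96).

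Example with t = 50%, q = 10%: rates 0.411 and 0.525, d = −0.114, SE = √((0.411×0.589 + 0.525×0.475)/300) = 0.0405, giving 3.5%. With q = 0 it is 2.5%.

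| t (assumed) | q = 10% | q = 20% |
|---|---|---|
| 30% | 3.1% | 3.7% |
| 50% | 3.5% | 4.8% |
| 70% | 4.0% | 6.1% |

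With t = 50% and q unequal (15% on MENOPUR, 20% on Gonal-f), the rates are 0.4265 and 0.55, d = −0.1235, and the error falls to 2.0%. The bias can go either way.

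**Effect of moving the primary bound to 56 elapsed days.** Suppose an assumed 5% or 10% of pregnancies in each arm were lost because the only scan came earlier. Rates of 0.361 and 0.475 give 3.5%; rates of 0.342 and 0.450 give 4.9%.

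**Scale.** At 150 v 150 of 300 the lower limit is −8.00 points. At 138 v 150 it is −11.99 (passes); at 137 v 150 it is −12.32 (fails). From equal rates of 50%, it takes a net change of 13 women to alter the conclusion.

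**The case against.** The strongest reply is that the text already excludes frozen cycles. Both estimators are defined for a single fresh cycle. After a negative test, Protocol 6.7 has luteal support stopped ("will be discontinued and EOT procedures completed") before any frozen transfer. Protocol 8.3 says "Pregnant subjects will complete their final study visit approximately 8-9 weeks after embryo transfer". Frozen-cycle outcomes are post-trial endpoints, and Protocol 9 says "A separate Statistical Analysis Plan will be prepared to cover the post-trial information". Women triggered with the agonist continue "with no fresh blastocyst transfer in order to decrease the risk of OHSS" (Protocol 6.4), so they have no fresh-transfer date and cannot meet the rule. All of this stands as evidence of intent. A reader might infer that frozen-cycle pregnancies will be counted and will inflate the error rate; the documents do not support that. The error rates above size an unlikely literal reading with assumed inputs. What remains is that the operative sentence leaves the exclusion to inference and ends at an undefined date.

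Second, a reader might infer that scans a full 8 days early are plainly admitted. That needs completed weeks, whereas SAP 9.2 declares an ordinal window of days 50 to 63. On ordinal weeks the gap to the 10th week is 0 to 1 day. The mismatch with the SAP's own day 50 remains on any reading.

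Third, a reader might infer that the rule lets in the visits held up to 4 weeks early. A visit 4 weeks before 56 elapsed days falls at 28, which stays excluded.

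Finally, the bound is not concealed: SAP 9.2 states it, and the change log announces the window. Only Section 12 omits it.

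**Conclusion.** The concern holds as a defect of specification. On the SAP's own count, the primary rule opens 1 to 2 days before the window that justifies it. On completed weeks it also opens before 10w0d: by 8 days on the documents' 2-week mapping, or by 3 if a 19-day offset is assumed. The rule does not say that the heartbeat must come from the fresh-transfer pregnancy, though that is very likely meant. The clinical-pregnancy timing conflicts with the protocol by one week, its bound opens 15 days before the protocol's 4 weeks, and Section 12 lists neither this change nor the early opening of the primary rule.

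The number of women affected is not given and is probably small. The documents give no ground for saying that the trial's conclusion would change. The case for correction is that these rules derive the primary endpoint and a key secondary endpoint, are inexact as written, and cost little to put right.

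**What to change.** Before database lock:

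- **Link.** In SAP 9.2, and likewise in 9.1.3, 9.3.1 and 9.3.2, count a heartbeat or positive result only if it belongs to the fresh-transfer pregnancy, with no frozen transfer before the assessment. Define the end of study. Keep accepting later scans of the same pregnancy.
- **Bound.** Make the formula start at day 50 and state whether days are counted from 1 or elapsed. In 9.2.1 add sensitivity analyses at the current 48 elapsed days and at the completed-week bound (56 elapsed days, or 51 if a 19-day offset is adopted). Do not make 56 the primary bound without a way to recover women scanned on days 50–55: that is inside the declared window, Table 1 schedules no scan after Visit 9, and later follow-up is by telephone or mail (Protocol 6.9).
- **Section 12.** Describe the heartbeat rule and its lower bound in place of the reference to a pregnancy test.
- **Clinical pregnancy.** Reconcile SAP 2.2 and 9.3.2 with Protocol 2.2, reset the day bound to match, and list any retained change in Section 12.

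The cost is a few sentences and a few lines of code, with no new data. Women whose only positive scan falls before the corrected bound become failures, so the reported rate may fall slightly. The sensitivity analyses will show by how much.
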